9.4.3 ANALYSIS OF THE SECONDARY ENDPOINT(S)

Secondary analyses are not dependent on results of primary endpoint. Similar ANCOVA models using data from both groups will be used to determine whether acupuncture treatments were associated with a significant change in MG ADL scores. Before analysis, MG ADL scores will be summarized at each timepoint using measures of center and spread as appropriate.

9.4.4 SAFETY ANALYSES

AE/SAEs will be reported as described in **Section 8.3** of this document. They will be classified by severity, relationship to study procedures, and expectedness. No other formal safety analyses will be conducted.

9.4.5 BASELINE DESCRIPTIVE STATISTICS

Baseline variables will be compared between groups to ensure randomization achieved balanced treatment assignments. This will include demographics (e.g. gender, age, race). All such variables are

listed in **Section 8.1** of this document. Variables will be summarized using descriptive statistics (e.g. mean and SD, or frequency and proportion) and compared inferentially. Continuous variables will be compared using two-sample t-tests or Wilcoxon rank tests and discrete variables will be compared using chi-square tests for independence or Fisher's exact tests.

9.4.6 PLANNED INTERIM ANALYSES

N/A

9.4.7 SUB-GROUP ANALYSES

Both primary and secondary outcomes will be descriptively summarized based on gender. Our sample size is unlikely to allow for other meaningful sub-group analyses.

9.4.8 TABULATION OF INDIVIDUAL PARTICIPANT DATA

N/A

9.4.9 EXPLORATORY ANALYSES

Exploratory outcomes (medications changes, treatment adherence) will be compared between groups with Student's t-test, Chi-square test, and Mann-Whitney-U test and mixed-model ANOVAs, as appropriate. As an exploratory analysis, patients who report post-COVID-19 symptoms will be identified using the additional COVID-19 set of questions. Types and severity of post-COVID-19 symptoms present within the group will be described. The t-test or non-parametric equivalent will be used to determine whether acupuncture had an effect on post-COVID symptoms.

If necessary, we will conduct a sensitivity analysis in which we exclude participants that had protocol deviations (e.g. large delays between treatments) due to illness, for example COVID-19.

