6.1.2 ADMINISTRATION AND/OR DOSING

Acupuncture Treatment Methods:

Group 1 will receive twice-weekly acupuncture immediately over 12-weeks. After a 12-week delay, Group 2 will also receive twice-weekly acupuncture over 12-weeks. Acupuncture treatments will be separated by a minimum of 2 days and a maximum of 14 days, unless a participant has an illness, such as COVID-19. In this case, additional time may be allowed, as determined by the investigator. Treatment methods will be identical for both groups and are described below.

Standard, sterile stainless-steel, disposable needles (DongBang™ Corporation, Spring Ten 0.22 x 30mm; Boryeoung, Republic of Korea) will be inserted in the acupuncture point locations (described below), with approximately 23-32 needles used for each treatment session. The number of needles used will be based

on the patient-reported symptoms. The depth of the needle insertion will be approximately 10-20mm, depending on the region of the body undergoing treatment. Needle reaction (soreness, numbness or distended feeling around the point, also known as a Deqi sensation) will occur during the initial insertion. Following 10 minutes of retention, some of the needles will be rotated in order to maintain Deqi sensation. Maintaining Deqi sensation has been shown to increase the effectiveness of acupuncture.^{10,11} All needles will be left in place for a total of 30 minutes, which is a typical duration in acupuncture practice.

Acupuncture points were selected for their classical Traditional Chinese Medicine indications relevant to MG symptom pathology, as well as their modern biomedical muscular, immunological, and neurological actions. The anatomical location for each point will be based on the World Health Organization's acupuncture point guideline.¹² Traditional Chinese manual acupuncture will be used at up to 32 acupuncture points. During treatment, acupuncture needles can be removed due to extreme pain or discomfort, so as not to exceed the removal of more than 4 needles.

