7.2 PARTICIPANT DISCONTINUATION/WITHDRAWAL FROM THE STUDY

Participants are free to withdraw from participation in the study at any time upon request. An investigator may discontinue a participant from the study for the following reasons:

1. Participant has not completed an acupuncture treatment for > 14 days, unless a participant has an illness, such as COVID-19. In this case, additional time may be allowed, as determined by the investigator.
2. Significant study intervention non-compliance
3. Lost-to-follow up; unable to contact subject (see **Section 7.3, Lost to Follow-Up**)
4. Any event or medical condition or situation occurs such that continued collection of follow-up study data would not be in the best interest of the participant or might require an additional treatment that would confound the interpretation of the study
5. The participant meets an exclusion criterion (either newly developed or not previously recognized) that precludes further study participation

The reason for participant discontinuation or withdrawal from the study will be recorded on the relevant eCRF. Subjects who sign the informed consent form and are randomized but do not receive the study intervention may be replaced. Subjects who sign the informed consent form, and are randomized and receive the study intervention, and subsequently withdraw, or are discontinued from the study, will not be replaced.

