10.1.10 PROTOCOL DEVIATIONS

This protocol defines a protocol deviation as any noncompliance with the clinical trial protocol. The noncompliance may be either on the part of the participant, the investigator, or the study site staff. As a result of deviations, corrective actions will be developed by the site and implemented promptly.

It will be the responsibility of the PI to use continuous vigilance to identify, document, and report deviations as soon as possible, but no later than 10 working days after identification of the protocol deviation. Minor deviations, which do not impact participant safety, compromise the integrity of study data and/or affect the participant's willingness to participate in the research are to be reported at the time of continuing review. Protocol deviations will be addressed in study source documents and sent to the reviewing IRB per their policies. The PI will be responsible for knowing and adhering to the reviewing IRB requirements.

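### Section 9.4.9 labels illness delays that the protocol lets the investigator allow as deviations, and its exclusion falls essentially on Group 1 alone, which can tilt this exploratory sensitivity analysis towards acupuncture

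*Combined protocol and SAP*

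**What the plan says.** Section 6.1.2 requires treatments to be "separated by a minimum of 2 days and a maximum of 14 days, unless a participant has an illness, such as COVID-19", and continues: "In this case, additional time may be allowed, as determined by the investigator". Section 7.2 gives as its first ground for discontinuation: "Participant has not completed an acupuncture treatment for > 14 days, unless a participant has an illness, such as COVID-19". It leaves discontinuation to the investigator's choice and repeats the allowance for illness. Section 10.2 says that visits are postponed when a participant screens positive for COVID-19. Section 10.1.10 "defines a protocol deviation as any noncompliance with the clinical trial protocol".

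Section 9.4.9 begins "If necessary, we will conduct a sensitivity analysis" and describes the exclusion: "exclude participants that had protocol deviations (e.g. large delays between treatments) due to illness". It does not define a large delay or when the analysis becomes necessary, and it does not name the comparison to be repeated. I read it as the primary one: change in MG-QOL15 over the first 12 weeks, with Group 1 treated and Group 2 untreated (9.4.2).

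**The concern.** Two things look wrong. First, an illness delay has two statuses: an allowed exception in 6.1.2 and 7.2, and the leading example of a deviation in 9.4.9. An analyst cannot tell who is to be excluded.

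Second, the marker for exclusion is a delay between treatments, and only Group 1 has treatments in the window that is compared. Illness could strike both groups equally, yet the ill would leave mainly one side. If illness worsens the score, Group 1 is left healthier than it was randomised and Group 2 is not. An analysis meant to test robustness to illness would then tend to support a benefit whether or not there is one.

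**Working it through.** **Status of an illness delay, section by section**

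- 6.1.2 and 7.2: a gap over 14 days is acceptable in illness, if the investigator allows the time.
- 10.2: after a positive COVID-19 screen, the protocol itself postpones the visit.
- 10.1.10: a deviation is noncompliance. A delay allowed under 6.1.2, or a postponement made under 10.2, is therefore not a deviation. An illness delay longer than the investigator allowed could be one.
- 9.4.9: large illness delays are given as deviations, with no distinction between allowed and not allowed.
- 7.3: refers to a 7-day maximum between visits, which does not agree with the 14 days in 6.1.2 and 7.2. This adds doubt about which gap counts.

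**What is recorded about illness in Group 2 during weeks 0-12**

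- The schedule in 1.3 has no adverse event reporting at Pre-treatment 2. The visit description limits that call to medication review and the two scales.
- 8.3.4 has a general sentence about documenting all events on study, but its explicit start date is the first acupuncture session. For Group 2 that comes after the 12-week wait.
- COVID-19 screening (10.2) takes place on clinic visit days. Group 2 has no clinic visit scheduled before its treatment starts.

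So a matching exclusion for Group 2 could not be rebuilt later from the planned data.

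**The plan's own power figures**

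Inputs from 9.2: 10 per group, two-sided 5%, difference 1.32 SD. The exact t-test has df = n1 + n2 − 2 = 18 and noncentrality (δ/σ) × √[n1·n2/(n1+n2)] = 1.32 × √5 = 2.95. Power is 79.7% (stated 80%). The attrition table, with δ = 9.5 and σ = 7, also reproduces: 71.4%, 77.1% and 81.9% for N = 16, 18 and 20 (stated 71%, 77%, 82%).

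**Size of the shift**

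The SD of 7 and the planned effect of 9.5 come from 9.2. The documents give neither an illness rate nor its effect on MG-QOL15, so both are assumptions. Let p be the illness rate in each arm, d the points that illness costs, q the share of ill Group 1 participants who are excluded, and let there be no treatment effect.

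- Mean illness cost in Group 2: p·d.
- Mean illness cost among those kept in Group 1: p·d·(1−q)/(1−p·q).
- Shift towards acupuncture: p·d·q·(1−p)/(1−p·q). With q = 1 this reduces to p·d.

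| p, d | q = 1 (ceiling) | q = 0.5 |
|---|---|---|
| 20%, 5 | 0.20 × 5 = 1.0 | 1.0 × 0.40/0.90 = 0.44 |
| 30%, 5 | 0.30 × 5 = 1.5 | 1.5 × 0.35/0.85 = 0.62 |
| 30%, 7 | 0.30 × 7 = 2.1 | 2.1 × 0.35/0.85 = 0.86 |

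Against the planned 9.5 points, 2.1 is 22% and 0.86 is 9%.

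Null simulation (40,000 trials per setting, SD 7, 10 per arm, t-test) gives two-sided error of 5.7%, 6.6% and 7.7% at q = 1, and 5.2%, 5.4% and 5.5% at q = 0.5. Because the bias has one direction, the share of false results favouring acupuncture is more telling. At q = 1 it is 4.5%, 5.8% and 7.3% (15,000 trials per setting), against a nominal 2.5%.

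**Loss of power from one-sided exclusion**

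Removing 1, 2 or 3 of 10 from Group 1 only leaves power of 77.3%, 74.3% or 70.7% at 1.32 SD.

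**The case against.** The strongest reply is that 9.4.9 asks a narrow and legitimate question, whether the result survives without illness-disrupted participants. It asks it only if needed, under an exploratory heading, and leaves the primary analysis alone. That stands, and it limits how much weight this point can carry.

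Three stronger readings are tempting and are not supported.

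- A reader might infer that the excluded set is empty, because an illness delay is never a deviation. The exception is at the investigator's discretion, so a delay beyond what was allowed can be one. By the same reasoning, not everyone excluded was compliant.
- A reader might infer that a Group 2 participant can never be excluded. Treatment delay is only an example of a deviation. A required call missed through illness could also qualify. The rule falls essentially on Group 1, but not by definition.
- A reader might infer that unexcused gaps over 14 days stay in the data. Section 9.4.9 does not remove them, but 7.2 permits discontinuation, 9.4.2 drops anyone without a 12-week score, and 9.3 plans a per-protocol analysis if attendance is poor. These provisions are optional or conditional, and the per-protocol set is undefined, so some such participants may remain.

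It may also be said that 9.4.9 mentions a set of COVID-19 questions. These are tied to post-COVID symptoms and have no row in the schedule of activities, so they cannot be relied on to record acute illness in Group 2.

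**Conclusion.** The point holds in a limited form. The status of an illness delay is contradictory across 6.1.2, 7.2, 9.4.9, 10.1.10 and 10.2. As written, the 9.4.9 exclusion acts on health essentially in one arm, with no record from which to match it in the other.

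Under the assumed rates and costs, the bias towards acupuncture is at most 1.0 to 2.1 points if every ill Group 1 participant is excluded, and about 0.4 to 0.9 points if half are. This rests on equal illness rates and equal illness effects in both arms, illness worsening MG-QOL15, no treatment effect, and 9.4.9 repeating the primary comparison. If illness does not affect the score, there is no shift. The primary result is untouched. The sponsor should correct this, but it does not threaten the trial's main conclusion.

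**What to change.** 1. Reconcile 6.1.2, 7.2, 7.3, 9.4.9, 10.1.10 and 10.2 so that an illness delay has one status and one gap limit applies throughout. Which clinical rule is right is for the investigators to decide.
2. At the week-12 call (Post-treatment 1 in Group 1, Pre-treatment 2 in Group 2), ask every participant the same question about COVID-19 or other acute illness since Visit 1.
3. Run the 9.4.9 analysis with that criterion applied to both arms. Use the answer on the call and not clinic-visit screening, because Group 1 attends clinic up to 24 times in the window and Group 2 does not. State in advance who is excluded and when the analysis will be run.
4. Report Group 1 treatment gaps over the agreed limit descriptively, split into those allowed for illness and the rest.

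The cost is some wording and one question on two existing calls. Anyone already past week 12 when the question is added will have no answer, and their number should be reported. A few more participants are lost: two from each arm gives 8 per group, the plan's own 71% row, against 76.6% if two are lost from Group 1 only (both at 9.5/7 SD). The analysis also still conditions on an event after randomisation, so it should stay labelled as exploratory.

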10 SUPPORTING DOCUMENTATION AND OPERATIONAL CONSIDERATIONS

10.1 REGULATORY, ETHICAL, AND STUDY OVERSIGHT CONSIDERATIONS

10.1.1 INFORMED CONSENT PROCESS

10.1.1.1 CONSENT/ASSENT AND OTHER INFORMATIONAL DOCUMENTS PROVIDED TO PARTICIPANTS

Consent forms describing in detail the study intervention, study procedures, and risks will be given to the participant and written documentation of informed consent will be completed prior to starting the study intervention. The following consent materials are submitted with this protocol:

- Study Volunteer Informed Consent Form
- Study Participant Informed Consent Form
- Study Participant HIPPA Authorization Form

- Recruitment Brochure
- Recruitment Flyer

10.1.1.2 CONSENT PROCEDURES AND DOCUMENTATION

At the end of the Pre-screening phone call, all eligible patients will be provided a copy of the consent and HIPPA forms via e-mail. Patients will also be provided an electronic copy of HealthPartners' statement of non-discrimination form. During the Pre-Treatment phone call, research staff will review the consent and HIPAA forms with the patients. Patients will be allowed time to review all documents and ask any questions prior to signing electronically. Research staff will confirm that the patients understand the information in the forms and answer any questions. To obtain signature, the e-consent framework in REDCap will be utilized. This framework allows the patient initials, date, time to be stamped in the footer as extra identity as to who is completing the consent and HIPPA documents. Following the consent conversation, the staff member will sign and e-mail the consent and HIPPA electronically to the patient. The patient will electronically sign, certify, and submit the consent and HIPPA in REDCap. A fully executed PDF copy of the consent and HIPPA will be provided electronically to the patient for their records as well as saved via the auto-archiver function in REDCap. Research staff will complete this process during the Pre-Treatment phone call, to ensure completion and assist if there are any questions.

10.1.2 STUDY DISCONTINUATION AND CLOSURE

This study may be temporarily suspended or prematurely terminated if there is sufficient reasonable cause. Written notification, documenting the reason for study suspension or termination, will be provided by the suspending or terminating party to study participants, investigators, the funding agency, the IRB and regulatory authorities. If the study is prematurely terminated or suspended, the PI will promptly inform study participants, the IRB, and the funding agency and will provide the reason(s) for the termination or suspension. Study participants will be contacted, as applicable, and be informed of changes to the study visit schedule.

Circumstances that may warrant termination or suspension include, but are not limited to:

1. Determination of unexpected, significant, or unacceptable risk to participants
2. Demonstration of efficacy that would warrant stopping
3. Insufficient compliance of study staff to the protocol (ie, significant protocol violations)
4. Data that are not sufficiently complete and/or evaluable
5. Determination of futility

The study may resume once concerns about safety, protocol compliance, and data quality are addressed, and satisfy the funding agency, IRB, or other relevant regulatory or oversight bodies.

10.1.3 CONFIDENTIALITY AND PRIVACY

Participant confidentiality and privacy is strictly held in trust by the participating investigators, their staff, the safety and oversight monitor(s), and the sponsor(s) and funding agency. This confidentiality is extended to the data being collected as part of this study. Data that could be used to identify a specific study participant will be held in strict confidence within the research team. No personally-identifiable information from the study will be released to any unauthorized third party without prior written approval of the sponsor/funding agency.

All research activities will be conducted in as private a setting as possible.

All study regulatory binders will be stored in a locked file cabinet within a secure office. The internal study monitor, representatives of the IRB, or regulatory agencies, may inspect all documents and records required to be maintained by the investigator, for the participants in this study. The clinical study site will permit access to such records.

The study participant's contact information will be securely stored at the clinical site for internal use during the study. At the end of the study, all records will continue to be kept in a secure location for as long a period as dictated by the reviewing IRB, Institutional policies, or sponsor/funding agency requirements.

Study participant research data, which is for purposes of statistical analysis and scientific reporting, will be password-protected and stored on REDCap, a secure web-based system. Only research study staff will have access to the data. Individual participants and their research data will be assigned a unique study identification number. While the study is active, subject identifiers (e.g. name, MRN) will be stored in REDCap, however, after the study is closed all subject identifiers will be removed.

The PI will ensure all mechanisms used to share data will include proper plans and safeguards for the protection of privacy, confidentiality, and security for data dissemination and reuse (e.g., all data will be thoroughly de-identified and will not be traceable to a specific study participant). Plans for archiving and long-term preservation of the data will be implemented, as appropriate.

10.1.4 FUTURE USE OF STORED SPECIMENS AND DATA

After the study is completed, the de-identified data will be and stored in REDCap for use in future research. Permission to keep the de-identified data will be included in the informed consent.

10.1.6 SAFETY OVERSIGHT

There is no Data Safety Monitoring Board for this study, as acupuncture has been previously shown to be safe and have minimal risks. During team meetings, the PI and study will review a rolling report of adverse events and report them appropriately.

10.1.7 CLINICAL MONITORING

N/A, refer to next section.

10.1.8 QUALITY ASSURANCE AND QUALITY CONTROL

Study staff will perform internal quality management of study conduct, data collection, documentation and completion.

Quality control (QC) procedures will be implemented as follows:

Informed consent --- Study staff will review both the documentation of the consenting process and 10% of the completed consent documents. Feedback will be provided to study staff to ensure proper consenting procedures are followed.

Source documents and the electronic data --- The majority of data will be directly entered into eCRFs in REDCap. To ensure accuracy for data not directly entered in REDCap, study staff will compare a representative sample of source data against the database, targeting key data points in that review.

Intervention Fidelity — Consistent delivery of the study interventions will be monitored throughout the intervention phase of the study. Procedures for ensuring fidelity of intervention delivery are described in **Section 6.2.1, Interventionist Training and Tracking**.

Protocol Deviations – The study team will review documented protocol deviations on an ongoing basis and will implement corrective actions when the quantity or nature of deviations are deemed to be at a level of concern.

We do not anticipate a need for independent monitoring for this study, however, should independent monitoring become necessary, the PI will provide direct access to all trial related sites, source data/documents, and reports for the purpose of monitoring and auditing by the sponsor/funding agency, and inspection by local and regulatory authorities.

10.1.9 DATA HANDLING AND RECORD KEEPING

10.1.9.1 DATA COLLECTION AND MANAGEMENT RESPONSIBILITIES

Data collection will be the responsibility of the research study staff under the supervision of the PI. The PI will be responsible for ensuring the accuracy, completeness, legibility, and timeliness of the data reported.

All data will be entered directly into eCRFs in REDCap. The data system includes password protection and internal quality checks by study staff to identify data that appear inconsistent, incomplete, or inaccurate. Treatment logs from the acupuncture treatment sessions will be scanned into and stored in REDCap.

